#### 11.0 STATISTICAL CONSIDERATIONS

### 11.1 Objectives and Design

This is a phase II study to investigate the efficacy of sunitinib in patients with advanced paraganglioma/ pheochromocytoma. The protocol will accrue up to 28 response evaluable patients. In order to minimize the expected number of patients treated in the event that the regimen proves to be very disappointing or very successful, a multistage design will be used for each cohort for patient accrual (Fleming T 1982).

### 11.2 Primary Endpoints and Analysis

The **primary end point** will be clinical benefit rate (CBR) which will be defined as either a partial response (PR) complete response (CR) or stable disease (SD) for  $\geq 12$  weeks. This will be measured using the Response Evaluation Criteria in Solid Tumors (RECIST) criteria.

### The **secondary end points** will be as follows:

- 1. Biochemical response as defined by a > 20% drop in one of; 24-hour urinary metanephrines, catecholamines or serum chromogranin A, and sustained for > 12-week period
- 2. Overall survival
- 3. Time to progression
- 4. Overall response rate (PR) + (CR)
- 5. tumour symptom improvement (descriptive)

NB: Response is defined as per the RECIST criteria as a 30% decrease in the sum of the diameters of the target lesions (partial response) maintained for at least 4 weeks, or complete disappearance of disease and cancer related symptoms (complete response), also maintained for at least 4 weeks. The 95% confidence interval for response rate will be calculated. The median and range of the duration of response will be assessed.

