### Every 12 weeks, end of every even cycle

- Chest x-ray or chest CT scan, if positive at baseline
- Abdominal and pelvic CT scan (or MRI), if positive at baseline
- Other x-rays/scans, if positive at baseline and as clinically indicated
- Clinical tumour measurements
- Urinary metanephrines, catecholamines or serum chromogranin A (at the end of approximately every 2 cycles)
- EKG; LVEF (MUGA) are only for patients with class II NYHA, prior anthracyclines or prior thoracic radiation

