#### 1.0 OBJECTIVES

1.1

To assess the efficacy (response rate) of sunitinib given orally daily for 4 out of every 6 weeks in patients with advanced or metastatic paraganglioma/ pheochromocytoma.

1.2

To assess the toxicity of sunitinib in patients with advanced or metastatic paraganglioma/ pheochromocytoma.

To document effects of sunitinib on markers of biochemical activity of advanced or metastatic paraganglioma/pheochromocytoma

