### 9.0 EVALUATION DURING AND AFTER PROTOCOL TREATMENT

### 9.1 Evaluation During Protocol Treatment

Investigation	Timing	Investigation	Timing
History and Physical Exam	Day 1 each cycle 	CBC, differential	Day 1 each cycle (prior to treatment) 
Weight, performance status 	Day 1  , 15, and 29 each cycle	PT/INR/PTT 	Twice weekly for first 3 weeks, then as clinically indicated
Clinical tumour measurements	End of every even numbered cycles	Biochemistry	Day 1 each cycle 
Blood pressure, heart rate 	Weekly for cycle 1  then Day 1  , 15, and 29 each cycle thereafter (assessed by nurse or home monitor)	BUN, serum creatinine/clearance  , sodium, potassium, chloride, bicarbonate, bilirubin, alkaline phosphatase, AST, ALT, LDH, total protein, calcium, phosphate, albumin, glucose, CPK	Day 1 each cycle 
Adverse Events/ Toxicity Evaluation 	Each visit at the end of every cycle	Amylase, Lipase	Day 1 each cycle 
Urinalysis	Day 1 each cycle 	TSH, T4	Day 1 each cycle 
EKG	Day 1 of even numbered cycles 	LVEF  / MUGA	Day 1 of even numbered cycles 
Endocrine testing (urinary metanephrines, catecholamines and serum chromogranin A)	Day 1, every 2 cycles 	CXR or CT 	End of even numbered cycles

Each visit:

 $^{1}$  Repeat daily if BP > 150/100 mmHg if previously WNL, OR recurrent, persistent (> 24Hrs) or symptomatic increase by > 20 mmHg and manage as per Section 8.3.

<sup>2 Only for patients receiving low dose anticoagulants (< 2 mg coumadin, warfarin) or LMW heparin.

 $^{3}$  Only required if serum creatinine is > ULN. Creatinine clearance to be measured directly by 24 hour urine sampling or as calculated by Cockcroft Formula: GFR = 1.04 x (140-age) x weight in kg NB: this version of the formula incorporates a 15% reduction for women

<sup>4 To ensure comparability, baseline xrays/scans/LVEF and subsequent xrays/scans/LVEF to assess response and cardiac effects must be performed using identical techniques.

<sup>5 Adverse events will be recorded and graded using NCI Common Terminology Criteria for Adverse Events Version 3.0 (CTCAE) (Appendix IV)

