### 10.2.5 RESPONSE

All patients will have their BEST RESPONSE on study classified as outlined below:

Complete Response (CR): disappearance of all target lesions. Pathological lymph nodes (whether target or non-target) must have reduction in short axis to < 10 mm.

Partial Response (PR): at least a 30% decrease in the sum of diameters of target lesions, taking as reference the baseline sum diameters.

Stable Disease (SD): steady state of disease. Neither sufficient shrinkage to qualify for PR nor sufficient increase to qualify for PD, taking as reference the smallest sum diameters while on study.

Progressive Disease (PD): at least 20% increase in the sum of diameters of target lesions taking as reference the smallest sum on study (includes baseline sum if that is smallest on study). In addition, the sum must also demonstrate an absolute increase of at least 5 mm. Appearance of new lesions will also constitute progressive disease. In exceptional circumstances, unequivocal progression of non-target lesions may be accepted as evidence of disease progression.

Response Criteria

Target	Non-Target	New	Overall	
Lesions	Lesions	Lesions	Response	
CR	CR	No	CR	
CR	Non-CR/Non-PD	No	PR	
CR	Not evaluated	No	PR	
PR	Non-PD or not all	No	PR	
	evaluated			
SD	Non-PD or not all	No	SD	
	evaluated			
Not all	Non-PD	No	NE	
evaluated				
PD	Any	Yes or No	PD	
Any	PD*	Yes or No	PD	
Any	Any	Yes	PD	

\* In exceptional circumstances, unequivocal progression in non-target lesions may be accepted as disease progression.

Note: Patients with a global deterioration of health status requiring discontinuation of treatment

without objective evidence of disease progression at that time should be reported as "symptomatic deterioration". Every effort should be made to document the objective progression even after discontinuation of treatment.

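### Response is defined differently in 10.2.5 and 11.2 (minimum duration, and symptoms in CR), and the plan does not say which governs the response rate or how an unconfirmed responder is classed

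*Combined protocol and SAP*

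**What the plan says.** **Section 10.2.5.** "All patients will have their BEST RESPONSE on study classified as outlined below". PR is "at least a 30% decrease in the sum of diameters of target lesions, taking as reference the baseline sum diameters". CR is "disappearance of all target lesions", with nodes below 10 mm in short axis; the table that follows also requires non-target CR. No duration, confirmation or symptom condition is given.

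**Section 11.2, the NB under the secondary end points.** PR is a "30% decrease in the sum of the diameters of the target lesions (partial response) maintained for at least 4 weeks". CR is "complete disappearance of disease and cancer related symptoms (complete response), also maintained for at least 4 weeks". A 95% confidence interval is to be calculated for the response rate, and the median and range of response duration reported.

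**Imaging.** Section 9.1 sets it at "End of even numbered cycles"; the trial summary says "Every 12 weeks, end of every even cycle". Note 12 to section 9.1 and note 15 to Appendix I allow responding or stable patients on treatment to move to every 4 months, plus or minus 2 weeks. Appendix I notes 10 and 12 require tumour measurement 4 weeks off protocol to confirm response in patients who leave with a PR or CR.

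**Where response is used.** Objective 1.1 is "To assess the efficacy (response rate) of sunitinib given orally daily for 4 out of every 6 weeks". In 11.2 the primary endpoint is the clinical benefit rate (CBR: CR, PR, or SD for at least 12 weeks) and the ORR is the fourth secondary endpoint. In 11.3 the final rule counts responses as defined by the CBR, but the stage 1 rule speaks only of no response.

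**The concern.** Both sections invoke RECIST, so the citation does not settle which one applies. If 10.2.5 governs, one scan at the 30% threshold makes a responder. If 11.2 governs, the shrinkage must also be shown to last. The CR definitions differ further on symptoms. In a tumour that can secrete catecholamines, symptoms and imaging need not move together, and the plan gives no rule for judging that symptoms have disappeared.

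The response rate is the efficacy measure named in objective 1.1. The trial is small, single-arm and open-label, and nothing in the plan provides for blinded or independent response review. If the definition is left open, it can be settled after the results are known.

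**Working it through.** The plan states no figure for the effect of the response definition, so there is none to reproduce. The check compares the definitions, tests whether the schedule can supply a confirming scan, and then sizes the effect.

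**1. Three constructed patients, baseline sum 100 mm**

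| Course | 10.2.5 | 11.2 NB | CBR |
|---|---|---|---|
| Week 12: 68 mm; week 24: 75 mm; no new lesions | PR (32% decrease) | Not shown: 25% decrease at the second scan | Counts either way |
| Week 12: 68 mm; no later scan | PR | Not stated | Counts as PR or, having reached 12 weeks, as SD |
| All lesions gone at weeks 12 and 24; symptoms persist | CR | Not CR; still meets the PR size criterion | Counts either way |

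The first patient has not progressed: (75 − 68)/68 = 10.3%, below the 20% threshold. The first two patients change the ORR. The third changes the split between CR and PR but not the ORR, provided the patient is then counted as a PR.

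**2. Can the schedule show 4 weeks of maintenance?**

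- Next scheduled scan: 2 cycles × 6 weeks = 12 weeks after the first response.
- Relaxed schedule: 4 × 52/12 = 17.3 weeks, plus or minus 2, so about 15 to 19 weeks.
- Off-study scan: 4 weeks off protocol.

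All are at least 4 weeks. A confirming scan is therefore available, but for a patient staying on treatment the working requirement is 12 weeks or more. A response held for 4 weeks and lost before the next scan cannot be verified.

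**3. Size for the ORR**

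One patient is 1/28 = 3.6 points. Exact (Clopper-Pearson) 95% intervals:

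| Responders | ORR | 95% CI |
|---|---|---|
| 5/28 | 17.9% | 6.1 to 36.9% |
| 4/28 | 14.3% | 4.0 to 32.7% |
| 3/28 | 10.7% | 2.3 to 28.2% |

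**4. Stage 1**

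The chance of no response in 14 is (1 − p)^14. The documents give no rate of failed confirmation, so a range is assumed, starting from an unconfirmed rate of 20%. This applies only if response at stage 1 means confirmed CR or PR.

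| Assumed share failing confirmation | Confirmed rate p | Chance of 0/14 |
|---|---|---|
| 0% | 20% | 0.044 |
| 10% | 18% | 0.062 |
| 20% | 16% | 0.087 |
| 30% | 14% | 0.121 |

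**5. What confirmation protects against (assumed illustration)**

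Simulation of 400,000 patients, each with a baseline and three follow-up sums, independent lognormal measurement error, and a fixed true shrinkage short of PR. Chance of reaching a 30% decrease:

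| True shrinkage | CV | Any one scan | Two consecutive scans |
|---|---|---|---|
| 20% | 5% | 7% | 1% |
| 20% | 8% | 25% | 6% |
| 20% | 10% | 34% | 10% |
| 10% | 5 to 10% | 0.1 to 9% | 0 to 1.3% |
| 0% | 5 to 10% | 0 to 1.6% | 0 to 0.1% |

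The 20% rows are a deliberately near-threshold case. The documents give neither the measurement CV nor the share of patients near the threshold, so the table does not estimate bias in this trial's ORR.

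**The case against.** The strongest reply is that the sections can be read together: 10.2.5 sets the size thresholds, 11.2 adds the duration, and Appendix I note 10 shows that confirmation was intended. On this reading a duration rule is already pre-specified. That is the more natural reading on duration, and it is the reason to align 10.2.5 with 11.2 rather than the reverse. It does not settle the matter: 10.2.5 classifies best response for all patients without reference to 11.2, the CR definitions still conflict on symptoms, and nothing says how a responder without a second scan is classed.

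A reader might also infer that the 4-week requirement cannot be checked because no scan could show it. The documents do not support that. The 12-weekly scans, the relaxed scans and the off-study scan all fall late enough. What is true is only that no scan is set at about 4 weeks for patients who stay on treatment.

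A reader might further infer that the primary result is at risk. In general it is not. Under 10.4, SD runs from the start of therapy to progression, and the first scheduled scan is at about 12 weeks, so an unconfirmed PR normally still counts in the CBR. Exceptions would be a PR on a scan before 12 weeks with no later assessment, or with early progression.

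**Conclusion.** The inconsistency is real and should be corrected, but its reach is limited. It affects mainly the secondary ORR (the response rate named in objective 1.1), its 95% interval, and which patients enter the duration-of-response summary, at 3.6 points per reclassified patient if 28 are evaluable. How many patients would be reclassified cannot be derived from the documents. The symptom clause affects the CR count rather than the ORR. The primary CBR is largely unaffected. Stage 1 is affected only if response there is read as CR or PR rather than as the CBR named in the final rule.

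**What to change.** Use one definition in 10.2.5 and 11.2:

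- Count a PR or CR in the ORR only if its criteria are still met on an assessment at least 4 weeks later, either the next scheduled scan or the off-study scan in Appendix I note 10.
- Class an unconfirmed PR or CR as SD if the SD criteria are met, otherwise as not evaluable, and keep the patient in the ORR denominator.
- Define CR by lesion criteria only. Tumour symptom improvement is already a separate descriptive endpoint.
- State in 11.3 whether response at stage 1 means the CBR, as it does in the final rule.

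The cost is text only; no new scans are needed. The ORR may be slightly lower. For patients staying on treatment, confirmation will in practice take 12 weeks, or about 15 to 19 weeks under the relaxed schedule, and the plan should say so.

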### 11.3 Sample Size and Duration of Study

Stage 1 of accrual: 14 response evaluable patients will be entered in the first stage. Using response hypotheses of H0 < 5% and Ha > 20%, we would reject the drug at the end of the first stage of accrual no response was seen. Otherwise, additional 14 patients will be accrued to the cohort.

Stage 2 of accrual: Additional 14 patients will be accrued. We would accept the drug as active if three or more responses (as defined by the CBR) are observed from 28 patients accrued.

Significance level and power: The procedure described above test the null hypothesis that the response rate is 5% versus alternating hypotheses that the response rate is 20%. The significance level (i.e., the probability of rejecting H0 when it is true) is  $\alpha$ =0.14 and the power (i.e., the probability of deciding the regimen is active) is 0.92 when true response rate is 20%. The expected sample size with this design is 28.

Accrual and duration of study

The estimated monthly accrual for this study is 1-2 patients a month. Thus, patient accrual is expected to be completed within 12-48 months. Additional time is required to allow the response data to mature.

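### Section 11.3 does not use one event: stage 1 stops on 'no response' and the hypotheses are worded as a 'response rate', while the final decision counts clinical benefit

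*Combined protocol and SAP*

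**What the plan says.** - **Primary endpoint (section 11.2).** It "will be clinical benefit rate (CBR) which will be defined as either a partial response (PR) complete response (CR) or stable disease (SD"); the stable disease must last at least 12 weeks. PR + CR is a secondary endpoint.
- **Meaning of response (note closing section 11.2, after the list of secondary endpoints).** "Response is defined as per the RECIST criteria as a 30% decrease in the sum of the diameters of the target lesions (partial response"). A CR also counts, and either has to persist for four weeks or longer. Stable disease is not part of it.
- **Objective 1.1.** "To assess the efficacy (response rate) of sunitinib given orally daily for 4 out of every 6 weeks".
- **Stage 1 (section 11.3).** After 14 evaluable patients, "we would reject the drug at the end of the first stage of accrual no response was seen". CBR is not mentioned here.
- **Stage 2 (section 11.3).** "We would accept the drug as active if three or more responses (as defined by the CBR) are observed from 28 patients accrued". This is the only sentence in the section that names CBR.
- **Hypotheses (section 11.3).** The procedure tests "the null hypothesis that the response rate is 5% versus alternating hypotheses that the response rate is 20" per cent, with a stated alpha of 0.14 and power of 0.92.
- **Sample size (section 11.3).** "The expected sample size with this design is 28". Section 11.1 gives the same number, 28, as the upper limit of accrual.

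**The concern.** This is the go/no-go rule on the primary endpoint, and its parts do not name the same event. Suppose the first 14 patients include no PR or CR but at least one with stable disease for 12 weeks or more. If stage 1 counts PR/CR, the drug is rejected. If it counts CBR, accrual continues to 28. The choice would be made in an open-label, single-arm trial once the data are known.

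The event also decides what the error rates mean. Alpha and power are quoted for a response rate, while acceptance is on CBR. If the two stages count different events, one pair of rates (5% and 20%) no longer describes the procedure, because its behaviour depends on two rates.

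**Working it through.** **Inputs.** From section 11.3: 14 + 14 patients, stop at 0 of 14, accept at 3 or more of 28, rates 5% and 20%, alpha 0.14, power 0.92, expected size 28. The documents give no SD rate and no no-drug CBR, so every CBR used below other than the plan's own 5% and 20% is an assumption.

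**1. The plan's own figures, one event in both stages at rate p.**
P(active) = Σ (x = 1 to 14) Bin(x; 14, p) × P(Bin(14, p) ≥ 3 − x). P(stop) = (1 − p)^14. Expected N = 28 − 14 × P(stop).

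At p = 0.05, the chances of 0, 1, 2 and 3 or more events in 14 are 0.4877, 0.3593, 0.1229 and 0.0301. In the second 14, P(≥ 2) = 0.1530 and P(≥ 1) = 0.5123. So P(active) = 0.3593 × 0.1530 + 0.1229 × 0.5123 + 0.0301 = 0.148. Expected N = 28 − 14 × 0.4877 = 21.2.

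At p = 0.20, the same chances are 0.0440, 0.1539, 0.2501 and 0.5519, with P(≥ 2) = 0.8021 and P(≥ 1) = 0.9560. So P(active) = 0.1539 × 0.8021 + 0.2501 × 0.9560 + 0.5519 = 0.914 with these rounded terms, and 0.9146 unrounded. Expected N = 28 − 14 × 0.0440 = 27.4.

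| | Stated | Exact |
|---|---|---|
| Alpha (5%) | 0.14 | 0.148 |
| Power (20%) | 0.92 | 0.915 |
| Expected N | 28 | 21.2 at 5%; 27.4 at 20% |

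Alpha matches only if truncated, and power is within a point. An expected size of 28 would require that the trial never stops at stage 1. These results are the same whichever single event is used, so the near-match cannot show which event was meant.

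**2. How often the two stage-1 readings disagree.**
With PR/CR rate o and CBR c ≥ o, they disagree when there is no PR/CR but at least one CBR event in 14: (1 − o)^14 − (1 − c)^14. At o = 0.05, (0.95)^14 = 0.4877:
- c = 0.10: 0.4877 − 0.2288 = 0.26
- c = 0.20: 0.4877 − 0.0440 = 0.44
- c = 0.30: 0.4877 − 0.0068 = 0.48

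**3. Stage 1 on PR/CR, final count on CBR.**
P(active) = P(Bin(28, c) ≥ 3) − (1 − o)^14 × S, where S is the chance of 3 or more CBR events in 28 given no PR/CR in the first 14: S = Σ (x = 0 to 14) Bin(x; 14, (c − o)/(1 − o)) × P(Bin(14, c) ≥ 3 − x).

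| o | c | P(Bin(28, c) ≥ 3) | (1 − o)^14 | S | P(active) |
|---|---|---|---|---|---|
| 0.05 | 0.05 | 0.1627 | 0.4877 | 0.0301 | 0.148 |
| 0.05 | 0.10 | 0.5406 | 0.4877 | 0.3617 | 0.364 |
| 0.05 | 0.20 | 0.9388 | 0.4877 | 0.9001 | 0.500 |
| 0.05 | 0.30 | 0.9962 | 0.4877 | 0.9934 | 0.512 |
| 0.01 | 0.20 | 0.9388 | 0.8687 | 0.9326 | 0.129 |

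P(active) cannot exceed 1 − (1 − o)^14, the chance of passing stage 1. That ceiling is 0.512 at o = 0.05 and 0.131 at o = 0.01. It equals 0.14 at o = 0.0107, so below a PR/CR rate of about 1.07% this mixed rule stays under 0.14 at any CBR.

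**4. CBR in both stages, no-drug CBR above 5%.**
The formula in step 1 gives P(active) = 0.50 at an assumed 10% and 0.78 at an assumed 15%.

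**The case against.** The strongest reply is that section 11.3 means CBR throughout and that the stage-1 sentence is merely loose. Much supports it. CBR is the stated primary endpoint, and this is its sample-size section. The hypotheses are introduced as those tested by the procedure just described, which ends in a CBR count over all 28 patients, stage-1 patients included. No sentence announces a change of event between stages. The note defining response follows the secondary endpoints and can be read as defining only overall response rate. On this reading the stated alpha and power are close to exact. I accept it as the better-supported reading.

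It does not settle the text. Objective 1.1 equates efficacy with response rate, section 11.2 defines response without stable disease, and the stage-1 sentence carries no qualifier. A stopping rule should not have to be inferred.

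A second reply concerns the null rate: any one-sided rule accepts more often when the true rate exceeds its null, so the probabilities at 10% and 15% are not errors in themselves. That stands. Entry under section 5.1.2 does allow symptomatic patients without documented progression. Evaluability under section 10.1.2 mostly requires two cycles, and section 10.4 counts SD from the start of therapy. These features suggest a no-drug CBR above 5%, but section 5.1.2 otherwise requires progression and asks investigators to try to document it. No figure is given. Part of the background section was also not available for this review, so the point is limited to what section 11 says.

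**Conclusion.** The section is wrong as written, in a limited way. The stage-1 rule and H0/Ha do not name the primary endpoint, and taken literally stage 1 can reject the drug while patients are meeting that endpoint. The probability of conflicting stage-1 decisions, 0.26 to 0.48, rests on an assumed PR/CR rate of 5% and CBR of 10% to 30%. The restated alpha, power and expected sample size need no assumption beyond the plan's own rule and rates; of these, only the expected size of 28 is materially off.

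Three stronger conclusions might be inferred, and the documents do not support them:
- **That the stated alpha and power fail outright.** They nearly hold with CBR throughout. They fail to describe the rule only if the stages use different events, and even then P(active) can fall below 0.14 at low PR/CR rates.
- **That 5% is the wrong null for CBR.** Section 11 gives no reason for it, which justifies a request, but no document gives a no-drug CBR.
- **That CBR should be replaced as primary endpoint.** Inconsistent wording is no ground for that. PR + CR remains a secondary endpoint, with a 95% confidence interval planned for the response rate.

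**What to change.** 1. In section 11.3, write CBR in the stage-1 stopping rule and in H0/Ha, so that both stages and the hypotheses refer to the endpoint in section 11.2.
2. Restate the operating characteristics of the 0/14, 3/28 rule: alpha 0.148, power 0.915, expected sample size 21.2 at a CBR of 5% and 27.4 at 20%, maximum 28.
3. As a request: justify 5% as the uninteresting CBR in this population, or state that the alpha applies only if the no-drug CBR is 5% or less.

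The cost is a wording amendment, with the Health Canada and ethics board review that section 15.3 requires, and slightly less favourable stated error rates. Items 1 and 2 change neither the number of patients nor the cut-offs. If the sponsor cannot support 5% under item 3, the caveat on alpha can stand without redesign.

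### Section 11.3 states a significance level of 0.14, but the exact value for its 0/14 then 3/28 rule is 0.148, so the false-positive rate is slightly understated

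*Combined protocol and SAP*

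**What the plan says.** Section 11.3 specifies the rule in full. At the first stage, "14 response evaluable patients will be entered in the first stage", and "we would reject the drug at the end of the first stage of accrual no response was seen". If the trial continues, "Stage 2 of accrual: Additional 14 patients will be accrued". At the end, "We would accept the drug as active if three or more responses (as defined by the CBR) are observed from 28 patients accrued". The procedure is said to "test the null hypothesis that the response rate is 5% versus alternating hypotheses that the response rate is 20" per cent.

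The error rates are attributed to that procedure. Alpha is defined in words, "The significance level (i.e., the probability of rejecting H0 when it is true) is", and the figures follow: "0.14 and the power (i.e., the probability of deciding the regimen is active) is 0.92 when true response rate is 20" per cent. The paragraph ends with an expected sample size of 28.

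Section 11.1 calls the design multistage, meant to limit accrual if the drug does very badly or very well. Section 11.3 gives a stopping rule for no activity only, and no early-success boundary.

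**The concern.** All the inputs are printed, so a reader should be able to reproduce both error rates from the text. Alpha cannot be reproduced at the stated precision: the exact value rounds to 0.15. The gap runs in the unhelpful direction, because the design already tolerates roughly a one-in-seven chance of calling an inactive drug active, and the stated figure makes that chance look slightly smaller than it is. What is at stake is the accuracy of a reported design property, not the conduct of the trial.

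**Working it through.** **Inputs, all from section 11.3.** First stage n1 = 14, stop if X1 = 0. Second stage n2 = 14, total 28. Active if X1 + X2 ≥ 3. Null rate 5%, alternative 20%. One assumption is added: the same event is counted at both stages.

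**Formula.** P(active | p) is the sum over x = 1 to 14 of P(X1 = x) × P(X2 ≥ 3 − x), with X1 and X2 independent Binomial(14, p). Equivalently, take the single-stage probability of at least 3 in 28 and remove the paths that the first-stage stop cuts off:

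P(active | p) = P(X ≥ 3 | 28, p) − P(X1 = 0) × P(X2 ≥ 3 | 14, p).

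**At p = 0.05**
- P(X ≥ 3 | 28) = 0.1627
- P(X1 = 0) = 0.95^14 = 0.4877
- P(X2 ≥ 3 | 14) = 0.0301
- Alpha = 0.1627 − 0.4877 × 0.0301 = 0.1627 − 0.0147 = **0.1480** (stated: 0.14)

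**At p = 0.20**
- P(X ≥ 3 | 28) = 0.9388
- P(X1 = 0) = 0.80^14 = 0.0440
- P(X2 ≥ 3 | 14) = 0.5519
- Power = 0.9388 − 0.0440 × 0.5519 = 0.9388 − 0.0243 ≈ **0.9146** (stated: 0.92; the unrounded terms give 0.91455)

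**Gaps.** Alpha: 0.148 − 0.14 = 0.008. Power: 0.92 − 0.9146 = 0.0054.

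**Could another reading of the rule give 0.14?**

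| Reading | Alpha | Power |
|---|---|---|
| As written: stop at 0/14, active at 3/28 | 0.148 | 0.915 |
| Adding early success at 3, 4 or 5 of 14 | 0.148 | 0.915 |
| Adding early success at 2 of 14 | 0.208 | 0.926 |
| Single stage, 3/28 | 0.163 | 0.939 |
| Stop at 1 or fewer of 14 | 0.093 | 0.791 |
| Final cut-off of 4 | 0.047 | 0.827 |
| Single stage 3/28, Poisson approximation | 0.167 | 0.918 |
| Single stage 3/28, normal with continuity correction | 0.170 | 0.928 |
| Single stage 3/28, normal without correction | 0.083 | 0.890 |

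The second row covers the very successful case mentioned in section 11.1. Three first-stage responses already meet the final cut-off, so stopping there changes neither figure. No row gives 0.14.

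**The case against.** The strongest reply is that this is a last-digit slip. Cutting 0.148 off at two decimals gives 0.14. Nothing that the trial does depends on the digit, and anyone content with an alpha of 0.14 has no evident reason to refuse 0.148. All of that stands, and it fixes the weight of the point. It does not make 0.14 correct, because the text defines alpha as a probability and the rule does not deliver that value.

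A reader might infer more than the documents support, in three ways.

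- **That both error rates are wrong and flattering.** The direction is the same for both, but 0.9146 written as 0.915 and then rounded up gives 0.92. A half-point difference of that kind is not a separate error.
- **That the two figures were taken from a different design.** A search over first-stage sizes 8 to 19, totals up to 35, first-stage cut-offs of 0 or 1 and final cut-offs of 2 to 4 finds one design that rounds to both: 16 then 27 patients in total, at 0.144 and 0.917. That contradicts the printed 14 and 28. The printed rule is itself within 0.01 of both figures, so truncation is the simpler explanation. The documents do not say how the figures were obtained.
- **That alpha and power are the only operating characteristics given.** Section 11.3 also states "The expected sample size with this design is 28". That is the maximum size. With the first-stage stop, the expected size is 14 + 14 × (1 − 0.4877) = 21.2 at 5 per cent and 14 + 14 × (1 − 0.0440) = 27.4 at 20 per cent. This is a different point, and the alpha correction does not rest on it.

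It can also be said that the calculation assumes one event throughout, whereas the first-stage sentence speaks of response and the final one refers to the clinical benefit rate. That is fair. The stated 0.14 and 0.92 also need some such assumption, so it should be written beside the corrected figures.

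**Conclusion.** The point holds for alpha, as a minor correction. The rule in section 11.3 has an exact one-sided false-positive rate of 0.148 at a 5 per cent response rate, against 0.14 stated: 0.8 of a percentage point, or about 6 per cent in relative terms (0.008 / 0.14). Truncation is the probable cause. Power is 0.915, and the stated 0.92 is acceptable as loose rounding. The result rests on the printed stage sizes and cut-offs, independent binary outcomes with a common rate, and the same event at both stages. No conclusion about sunitinib's activity would change.

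**What to change.** In section 11.3, restate the significance level as 0.148 (0.15) and, so that both figures follow one rounding convention, the power as 0.915 (0.91). Add that both are exact binomial values for the two-stage rule when the same event is counted at each stage. Leave the stage sizes, the two cut-offs and the 5 and 20 per cent hypotheses unchanged. The cost is one amended sentence, with no effect on sample size, conduct or decisions; two published figures become very slightly less favourable.

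### Section 11.3 understates the significance level (0.14 stated, 0.148 exact) and gives the maximum of 28 as the expected sample size; Section 11.1 claims a saving for a very successful regimen that the rule does not give

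*Combined protocol and SAP*

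**What the plan says.** Section 11.1 sets the ceiling: "The protocol will accrue up to 28 response evaluable patients". It gives the reason for a multistage design as limiting the number treated in the "event that the regimen proves to be very disappointing or very successful".

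Section 11.3 gives the rule:

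- Stage 1: "14 response evaluable patients will be entered in the first stage".
- Stop: "we would reject the drug at the end of the first stage of accrual no response was seen". I read this as stopping if no response is seen in the first 14.
- Continue: "Otherwise, additional 14 patients will be accrued to the cohort".
- Final decision: "We would accept the drug as active if three or more responses (as defined by the CBR) are observed from 28 patients accrued".

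The rates tested are 5% (null) and 20% (alternative). The section then reports three operating characteristics: a significance level of 0.14, power of 0.92 at a true rate of 20%, and the sentence "The expected sample size with this design is 28". That last sentence names no true response rate.

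**The concern.** There are three linked problems in the description of the design.

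1. **Significance level.** Section 11.3 says what the number means ("The significance level (i.e., the probability of rejecting H0 when it is true) is" 0.14), and it fixes both stage sizes, both cut-offs and the null rate. The value is therefore an exact binomial probability that anyone can check, and 0.14 is lower than the rule delivers.
2. **Expected sample size.** A design that can stop at 14 cannot have an expectation equal to its maximum of 28 unless the chance of stopping is zero. Quoting 28 with no true rate attached makes the interim look seem to save nothing. It does save patients in the case it was built for, an inactive drug.
3. **Rationale against rule.** Section 11.1 promises a saving at both extremes. Section 11.3 has a stop at one extreme only.

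An ethics board or reader judges a single-arm phase II design by its significance level, expected size and probability of early termination. Here the first is too favourable, the second is unlabelled, and the third is not given.

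**Working it through.** **Inputs (all from Section 11.3):** stage sizes n1 = n2 = 14; stop if X1 = 0; declare active if X1 + X2 ≥ 3; p0 = 0.05; p1 = 0.20. X1 and X2 are independent Binomial(14, p).

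**Formulas**

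- Probability of early termination: PET(p) = (1 − p)^14.
- Probability of declaring the drug active: the single-stage probability of at least 3 in 28, less the paths on which stage 1 had no response and the trial stopped: P(active) = P(Bin(28, p) ≥ 3) − PET(p) × P(Bin(14, p) ≥ 3).
- Expected size: E[N] = 14 + 14 × (1 − PET(p)) = 28 − 14 × (1 − p)^14.

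**Power, stated 0.92.** At p = 0.20: PET = 0.80^14 = 0.0440, and P(active) = 0.9388 − 0.0440 × 0.552 = 0.9146. This rounds to 0.91 but is close to the stated figure, and I do not contest it.

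**Significance level, stated 0.14.** At p = 0.05: PET = 0.95^14 = 0.4877, and P(active) = 0.1627 − 0.4877 × 0.030 = 0.1480. The stated figure is not reproduced. Other ways of computing it with 14 + 14 patients do not give 0.14 either:

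| Calculation | Significance level |
|---|---|
| Two-stage exact, as written | 0.148 |
| Single-stage exact, ≥3 of 28 | 0.163 |
| Poisson, mean 1.4 | 0.167 |
| Normal approximation, without / with continuity correction | 0.083 / 0.170 |
| Success stop added at ≥3 or ≥4 of 14 | 0.148 |
| Success stop added at ≥2 of 14 | 0.208 |
| Final cut-off ≥2 / ≥4 of 28 | 0.337 / 0.047 |

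Of the nearby stage sizes tried, three round to 0.14 (14 + 13: 0.1385; 13 + 15: 0.1441; 12 + 16: 0.1395), but none is the plan's. Truncating 0.148 gives 0.14, but truncating 0.9146 gives 0.91, so no single convention yields both printed figures.

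**Expected size, stated 28**

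| True rate | PET | E[N] | Saving against 28 |
|---|---|---|---|
| 5% | 0.4877 | 21.17 | 6.8 |
| 20% | 0.0440 | 27.38 | 0.6 |
| 40% | 0.0008 | 27.99 | 0.01 |

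E[N] is below 28 at any rate under 100% and rises with activity.

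**The claim about a very successful regimen.** The probability that the final criterion (three responses) is already met within the first 14 patients is 0.030 at 5%, 0.552 at 20% and 0.960 at 40%. In each of those cases Section 11.3 still enrols 14 more.

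**What a success stop would do, if one were wanted.** Three responses in 14 already satisfy three in 28, so stopping at ≥3 of 14 changes no decision: the significance level stays at 0.148 and power at 0.915. The probability of stopping at 14, for either reason, becomes 0.5177 at 5% and 0.5959 at 20%. Then E[N] = 14 + 14 × 0.4823 = 20.8 and 14 + 14 × 0.4041 = 19.7. The cost of ending at 14 instead of 28:

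- The standard error of a 20% rate rises from √(0.16/28) = 7.6 to √(0.16/14) = 10.7 percentage points.
- The chance of seeing at least one adverse event of 5% incidence falls from 1 − 0.95^28 = 76% to 1 − 0.95^14 = 51%.

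**The case against.** The strongest reply is that these are reporting slips. The gap in the significance level is 0.8 percentage points, and a reader content with 14% would not decide differently at 14.8%. The sentence on expected size directly follows the power at a 20% rate, so 28 could be the alternative-hypothesis value of 27.38 rounded up to whole patients. The rule in Section 11.3 is clear, so nobody running the trial would infer a success stop from a phrase in Section 11.1. Full accrual also serves the confidence interval and the toxicity objective. Finally, 21.2 is itself conditional. Section 11.3 mentions no pause after patient 14. Stable disease needs 12 weeks, and accrual is one to two patients a month, so about 3 to 6 more could enter before 0 of 14 is known. That would put the null expectation at 21.17 + 0.4877 × 3 = 22.6 to 21.17 + 0.4877 × 6 = 24.1.

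Much of this stands. The decision rule is unaffected, a futility-only design is an ordinary choice, and the basis of the expected size should be stated. It does not rescue the text. The stated level is still not what the rule gives. If 28 is meant for a 20% rate, it needs that label, 27.38 rounds to 27, and the null value is still missing. Even with the overrun, the null expectation is well short of 28. The rationale in Section 11.1 still describes a saving that the rule does not provide.

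**Conclusion.** The point holds in all three parts. The exact one-sided significance level is 0.148 against 0.14 stated. Expected size is 21.2 under the null and 27.4 under the alternative, against an unlabelled 28 that equals the maximum. The reference to a very successful regimen has no counterpart in the rule. The stated power is acceptable.

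The practical weight is moderate: no stage size, threshold or decision changes, and the largest discrepancy is the 6.8 patients under the null.

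The figures rest on the rule as written, independent patients with a common response probability, counts of response-evaluable patients, and no enrolment beyond 14 until stage 1 is read. The significance level is taken at 5%, the null rate Section 11.3 tests; at lower rates the probability is smaller (0.142 at 4.9%). Whether 5% and 20% suit an endpoint that counts stable disease is a separate question, not examined here.

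**What to change.** In Section 11.3, replace the stated operating characteristics with:

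- one-sided significance level 0.148 (true rate 5%);
- power 0.915 (true rate 20%);
- probability of stopping after stage 1 under the null, 0.49;
- expected size 21.2 at 5% and 27.4 at 20%, in response-evaluable patients and assuming no enrolment beyond 14 until stage 1 is read;
- maximum size 28.

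In Section 11.1, delete the three words that refer to a very successful regimen.

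The cost is one paragraph and three words. No patients are added, the stage sizes and the three-of-28 threshold stay, and the stated significance level becomes slightly less favourable.

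Only if the sponsor actually wants an early-success stop should those words stay, and then the boundary must be pre-specified in Section 11.3. A stop at three or more of 14 would leave the significance level and power unchanged, with the loss of precision and safety data shown above. The correction does not depend on it.
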